Participants may experience the potential risk of COVID-19 transmission during required in-person study visits such as at the Biomedical Research Imaging Center (BRIC) and when in close contact with study team members during Lupron injections or blood draws when study staff will need to maintain less than 6ft distance. The study team will be following UNC guidelines and BRIC guidelines to take every possible precaution to protect study participants and their staff. Including virtual video or telephone visits when possible, shortening duration of in-person contact, requiring masks at all times for study staff and participants, maintaining 6ft distance when possible, temperature checks on arrival to BRIC, COVID-19 pre-screening 24 hours in advance of any in-person contact and the day of, frequent cleaning with 90% alcohol or 1:10 bleach solution, cleaning equipment between each participant, handwashing required every hour and before or after contact with any participants. While the study team will be taking every pre-caution possible to participants and the study staff there may still be a risk of COVID-19 transmission due to the possibility of the COVID-19 virus lingering in enclosed spaces from asymptomatic carriers. However this risk should not be any greater than being in an essential public setting such as a grocery store. If a participant or a member of the study team has had direct or even secondary contact with any suspected or confirmed cases of COVID, the study team will reschedule any upcoming visits until the case is confirmed negative or to quarantine for at least 14 days and monitor symptoms. If a participant or study team member experiences any symptoms of COVID-19 including but not limited to: cough, fever, chest pain, trouble breathing, loss of smell or taste, nausea, abdominal pain, vomiting, etc. participants will be asked to notify the study team immediately, contact their Primary Care Provider and their local COVID-19 hotline to get tested for COVID-19.

2 Study Objectives

The objective of the current project is to extend this line of work by examining whether hormone sensitive women (HS+; n=15) show differences in the behavioral activation system relative to non-hormone sensitive women (HS-; n=15) under baseline and hormone challenge conditions using functional magnetic resonance imaging (fMRI) and behavioral tests. Our central hypothesis is that reproductive hormone changes are associated with dysregulated threat and reward processing and consequent irritability in HS+. The rationale for the proposed study is that employing a scaled down model of puerperal hormonal events permits the identification of a group of individuals homogeneous for hormone sensitivity (HS+), hence creating the best opportunity for disentangling the specific changes in brain function due to reproductive hormones (i.e., HS-) from those accompanying reproductive hormone-precipitated affective dysfunction (i.e., HS+). Because women will act as their own controls across time, this study design also allows for a powerful evaluation of state and trait variables that may contribute to irritability, including both threat processing and reward processing. Identifying both state and trait markers of irritability, and disentangling them from the effects of reproductive hormones on brain and behavior, will allow for the identification of neural substrates of irritability susceptibility that can be investigated across neuropsychiatric disorders. We plan to accomplish the objectives of this application by pursuing the following specific aims:

Aim 1: To determine the extent to which irritability is characterized by dysfunctional threat processing during reproductive hormone challenge relative to baseline in HS+ and HS-.

Hypothesis 1: We hypothesize that HS+ is characterized by behavioral activation in the context of potential threat. Given this hypothesis, we expect that:

Hypothesis 1a: Compared with HS-, HS+ will show a greater degree of threat attention bias as measured by the visual dot probe task during hormone addback relative to baseline.

Hypothesis 1b: Compared with HS-, HS+ will show reduced amygdala-medial PFC connectivity in response to threatening stimuli during hormone addback relative to baseline.

Hypothesis 1c (secondary): HS+ will show a significant association between self-reported irritability and 1) threat attention bias, and 2) amygdala-ventrolateral PFC connectivity during hormone addback.

Aim 2: To determine the extent to which irritability is characterized by dysfunctional reward processing during reproductive hormone challenge relative to baseline in HS+ and HS-.

Hypothesis 2: We hypothesize that HS+ is characterized by increased frustration in the context of non-reward (i.e., when reward is expected). Given this hypothesis, we expect that:

Hypothesis 2a: Compared with HS-, HS+ will show greater reactive aggression assessed with the Point Subtraction Paradigm during hormone addback relative to baseline.

Hypothesis 2b: Compared with HS-, HS+ will show reduced activation of the amygdala and ventral striatum in response to FNR during hormone addback relative to baseline.

Hypothesis 2c (secondary): HS+ will show a significant association between self-reported irritability and 1) reactive aggression, and 2) striatal activation during hormone addback.

3 Study Design

3.1 General Design

This is a double-blind, placebo controlled, longitudinal cohort-comparison study, single-center study using Lupron depot, estradiol, and progesterone to examine whether hormone sensitive women (HS+; n=15) show differences in the behavioral activation system relative to non-hormone sensitive women (HS-; n=15) under baseline and hormone challenge conditions using functional magnetic resonance imaging (fMRI) and behavioral tests. This study will include 8 study visits, and the hormone protocol will last 8 weeks. Out of those 8 visits, 2 of them will require subjects to come to UNC's campus for their MRI visits at BRIC, while the rest of the appointments will be done virtually through HIPAA compliant Zoom, Webex, or phone when zoom is not available. Out of these 6 virtual visits, 2 of them will require brief in-person contact for phlebotomy or an IM injection of Lupron, these very brief points of contact will be performed outside the subject's home when possible (i.e. backyard, back porch, or screened porch). In the context of COVID-19, all participants and staff will complete the appropriate screening as recommended by UNC and BRIC policy prior to any in-person contact. During in person visits participants and the study team will be required to wear masks at all times and maintain 6 feet distance when possible to minimize the possibility of COVID-19 transmission. Participants will undergo a scaled down hormonal model of pregnancy and parturition (using ovarian suppression with the GnRH agonist Lupron and hormone addback with E2 and progesterone P4) in order to examine how hormones influence neural function and irritability in experimentally confirmed HS+ and HS-. FMRI sessions will occur at baseline and following two weeks of hormone addback. The study timeline is depicted in **Figure 6**, and the specific procedures that will take place are outlined in **Table 1** and detailed below in Section 6.

[figure not shown]

Figure 6. Protocol Timeline. Symbols: fMRI session. The timeline shown displays the 12 week study, time points of each medication to be administered along with the phase of the study which it occurs.

3.2 Outcome Variables

The primary endpoints for this aim are 1) threat attention bias assessed during the visual dot-probe paradigm, 2) amygdala-medial PFC connectivity in response to threatening faces on the implicit emotion face processing task in HS+ (compared with HS-) during hormone challenge relative to baseline. The secondary endpoints for this aim are the 1) correlation between IDAS-II irritability and threat attention bias, and 2) correlation between IDAS-II irritability and amygdala-medial PFC connectivity in HS+.

4 Subject Selection and Withdrawal

4.1 Inclusion Criteria

Participants will enroll healthy, euthymic 21-45 year old women with a history of postpartum depression ($n=23$) and women without such a history ($n=16$). Only participants capable of giving informed consent will be enrolled. Participants will be compensated upon completion of the study.

Inclusion Criteria.

Group 1: Women with a history of postpartum depression

- 1) A history of a DSM-V major depression episode that occurred within 6 weeks of childbirth (as determined by a SCID interview) and remitted at least one year prior to enrollment in the study;
- 2) Has been well for a minimum of one year;
- 3) A regular menstrual cycle for at least three months;
- 4) Age 21-45;
- 6) Medication free (including birth control pills);

Group 2: Healthy Controls

- 1) Controls will meet all inclusion criteria specified above.

A structured clinical interview for DSM-V (SCID) will be administered to all women prior to study entry. Any woman with a current axis I psychiatric diagnosis will be excluded from participating in this protocol.

4.2 Exclusion Criteria

Patients will not be permitted to enter this protocol if they have important clinical or laboratory abnormalities including any of the following:

- current axis I psychiatric diagnosis (based on a structured clinical interview for DSM-V (SCID));
- endometriosis;
- undiagnosed enlargement of the ovaries;
- liver disease;
- breast cancer;
- a history of blood clots in the legs or lungs;

- undiagnosed vaginal bleeding;
- porphyria;
- diabetes mellitus;
- malignant melanoma;
- gallbladder or pancreatic disease;
- heart or kidney disease;
- cerebrovascular disease (stroke);
- cigarette smoking;
- a history of suicide attempts or psychotic episodes requiring hospitalization;
- recurrent migraine with aura;
- pregnancy-related medical conditions such as hyperemesis gravidarum, pretoxemia and toxemia, deep vein thrombosis (DVT) and bleeding diathesis;
- Any woman with a first degree relative (immediate family) with premenopausal breast cancer or breast cancer presenting in both breasts or any woman who has multiple family members (greater than three relatives) with postmenopausal breast cancer will also be excluded from participating in this protocol;
- Any woman meeting the Stages of Reproductive Aging Workshop Criteria (STRAW) for perimenopause will be excluded from participation. Specifically, we will exclude any woman with an elevated plasma FSH level (> 14 IU/L) and with menstrual cycle variability of > 7 days different from their normal cycle length.
- Pregnant women will be excluded from participation (patients will be warned not to become pregnant during the study and will be advised to employ barrier contraceptive methods), and women who become pregnant (although unlikely because of the hormone manipulation) will be withdrawn. The use of leuprolide acetate is not recommended during pregnancy. Prior to treatment, a complete physical, including a serum β -HCG test for pregnancy. Participants will be seen at the outpatient clinic on a regular biweekly basis. All participants will be required to use non-hormonal forms of birth control (e.g., barrier methods) to avoid pregnancy during this study. Participants will also undergo urine toxicology and pregnancy tests on the day of each of the two fMRI scans. If a woman becomes pregnant during the study, she will not complete the fMRI scan, and the hormone protocol will be discontinued.

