Progesterone is synthesized from a starting material from a plant source and is chemically identical to progesterone of human ovarian origin. PROMETRIUM Capsules are available in multiple strengths to afford dosage flexibility for optimum management. PROMETRIUM Capsules contain 100 mg or 200 mg micronized progesterone.

The inactive ingredients for PROMETRIUM Capsules 100 mg include: peanut oil NF, gelatin NF, glycerin USP, lecithin NF, titanium dioxide USP, D&C Yellow No. 10, and FD&C Red No. 40.

The inactive ingredients for PROMETRIUM Capsules 200 mg include: peanut oil NF, gelatin NF, glycerin USP, lecithin NF, titanium dioxide USP, D&C Yellow No. 10, and FD&C Yellow No. 6.

Pharmacology

PROMETRIUM Capsules are an oral dosage form of micronized progesterone which is chemically identical to progesterone of ovarian origin. The oral bioavailability of progesterone is increased through micronization.

Summary of Previous Human Experience

The proposed monthly 3.75-mg injection of leuprolide acetate (Lupron Depot) is FDA-approved for use in premenopausal women to treat endometriosis and uterine fibroids. Lupron has also been widely researched in healthy premenopausal women (Flory et al., 2002; Grigorova et al., 2006; Matthews et al., 1998; Sánchez et al., 2002) and to treat a variety of conditions, including ovarian epithelial tumor cells (Thompson et al., 1991), insulin resistance (Elkind-Hirsch, Valdes, & Malinak, 1993), endometrial stromal sarcoma (Scribner Jr. & Walker, 1998), and infertility (Padilla et al., 1991).

Several studies have investigated the use of Lupron and hormone addback to treat the symptoms of premenstrual syndrome and premenstrual dysphoric disorder (Lee et al., 2012; Mitwally et al., 2002; Schmidt et al., 1998; Wyatt et al., 2004), which has resulted in combined Lupron and estrogen/progestin supplementation as a recommended long-term treatment for premenstrual syndrome (Kaur et al., 2004; Mezrow et al., 1994).

Healthy women undergoing in vitro fertilization (IVF) routinely receive luteal supplementation of 600 mg progesterone daily along with 6 mg oral micronized estradiol (Lukaszuk et al., 2005) in combination with GnRH agonists (e.g., Lupron).

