Progesterone: Progesterone and the synthetic progestins are widely prescribed, with indications including dysfunctional uterine bleeding, endometriosis, mastodynia, galactorrhea, and precocious puberty (Henzel, 1986). Side effects reported in women taking progestins may include breakthrough bleeding, edema, change in weight (increase or decrease), cholestatic jaundice, rash (with or without pruritus), depression, easy fatigue and sedation, lack of initiative, and chloasma. Since progestins are often used in women with antecedent menstrual irregularity, it is not clear whether the breakthrough bleeding represents an effect of the medication or refractoriness to treatment. In the large majority of patients, menstruation occurs predictably following withdrawal of progestins and is usually more regular than in spontaneous cycles. In a recent study, an average dose of 1750 mg of oral micronized progesterone was given to 59 women with PMS for a period of three months and was well tolerated by this sample. The side effects reported on progesterone were lightheadedness, fatigue, forgetfulness, and headaches. These were very mild and caused no dropouts.

For the sake of completeness, we will also describe the side effects reported when estradiol and progesterone are combined in the form of oral contraceptives. Side effects observed in patients receiving combined oral contraceptives include nausea, breast soreness, vaginal discharge, fluid retention, hypertension, and clotting abnormalities that have been associated with the estradiol component of the oral contraceptive. Thromboembolic disorders including thrombophlebitis, pulmonary

embolism, and cerebral and coronary thrombosis appear to occur with greater frequency in women taking oral contraceptives. While the increased incidence of these disorders has been associated with the estradiol component of the oral contraceptives, it is now believed that the progestogen component may, to a lesser extent, contribute to the increased risk. There are relatively few reports associating oral contraceptives with the development of carcinomas (vaginal, uterine, hepatic, and mammary) despite the vast use of these agents, although this may reflect the latent period needed for cellular transformation. Finally, several reports suggest an association between intrauterine exposure to female sex hormones and congenital anomalies.

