The prior protocol most relevant to the current proposal is the trial we completed most recently, which used higher doses of hormones (at least twice the doses of both E2 and P4 proposed here) and for a longer duration (8 weeks versus 2 weeks) and was classified as IND exempt by the FDA. To clarify differences between the protocol described in our IND application and that proposed here, we have summarized the medication regimens in the table below.

Table 2. Medication Regimens in previous IND Exempt Protocol and the Proposed Protocol

	Past IND Exempt Protocol				Current Protocol		
Phase	1: Hypogonadism	2: Low Dose Addback	3: High Dose Addback	4: High Dose Withdrawal	1: Hypogonadism	2: Low Dose Addback	3: Low Dose Withdrawal
Duration	4 weeks	2 weeks	6 weeks	4 weeks	4 weeks	2 weeks	2 weeks
Lupron	3.75 mg IM dose #1	3.75 mg IM dose #2	3.75 mg IM dose #3	3.75 mg IM dose #4	3.75 mg IM dose #1	3.75 mg IM dose #2	N/A
Estrace	Placebo	2 mg bid	5 mg bid	Placebo	Placebo	2 mg bid	Placebo
Prometrium	Placebo	200 mg bid	400 mg bid	Placebo	Placebo	200 mg bid	Placebo

Below (Table 3) is a list of the adverse events that occurred in the previous, IND exempt protocol conducted at UNC using the same hormone protocol as that proposed in the current study. We have listed the adverse events that occurred during phases 1 and 2 (highlighted in yellow), which involved administration of medications, doses, and durations that are identical to those proposed in the current study, separately from those that occurred in phases 3 and 4 (highlighted in blue), which involved Estrace and Prometrium administration and withdrawal from doses that were at least twice those proposed in the current study and durations that were three times as long.

Table 3. Adverse Events in the Previous IND Exempt Protocol

	1: Hypogonadism	2: Low Dose Addback	3: High Dose Addback	4: High Dose Withdrawal	5: Follow-up	TOTAL
Cognitive:						
Drowsiness	1	1	4	1		7
Sedation		3	4			7
Dizziness	1	5	3			9
Lightheadedness		1	4			5
Memory impairment			1			1

Psychological:						
Depression		2	2			4
Anxiety		1				1
Irritability		2			1	3
Mood Swings		1	1			2
Trouble concentrating	1					1
Night Terrors		1				1
Gastrointestinal:						
Nausea		1	1			2
Diarrhea	1					1
Upset Stomach				1		1
Constipation	1				1	2
Heart Burn	1	1				2
Cardiac:						
Transient Heart Palpitations*	1					1
Chest Pain*		1	1			2
Arrhythmia*	1					1
Bradycardia*	1					1
Menstrual:						
Spotting	1		3			4
Prolonged menstrual bleeding			1	1		2

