- Participants will complete a safety questionnaire to determine whether they have any foreign iron or steel metal objects in their bodies, such as a pacemaker, shrapnel, metal plate, or metal debris. If they have any such objects in their bodies, they cannot participate in the MRI session.
- All participants will receive a pregnancy test and urine drug screening. No pregnant women will be entered into the study, because the study drugs (Lupron, estrogen, and progesterone) may be associated with birth defects.

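### In the text we can see, no pregnancy test is scheduled at Visit 5, when the second Lupron dose is given; adding one is a modest, cheap safety gain

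*Combined protocol and SAP*

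**What the plan says.** Testing before treatment: Section 4.2 calls for a serum β-hCG, which Appendix C (Study Design) places at Visit 2. Section 4.3 lists a pregnancy test for all participants at screening.

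Testing on study, in Section 4.2 and repeated in Appendix C: "Participants will also undergo urine toxicology and pregnancy tests on the day of each of the two fMRI scans". Table 1 puts the scans at Visits 3 and 6.

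Dosing: Section 6 gives Lupron at Visits 3 and 5, the first at the end of Visit 3 and the second a month later. Active estradiol (4 mg/day) and progesterone (400 mg/day) follow the month of Lupron alone and run over weeks 4 to 6 (Section 5.2).

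Other safeguards in Section 4.2: "All participants will be required to use non-hormonal forms of birth control (e.g., barrier methods) to avoid pregnancy during this study". It also states that "women who become pregnant (although unlikely because of the hormone manipulation) will be withdrawn", and that "If a woman becomes pregnant during the study, she will not complete the fMRI scan, and the hormone protocol will be discontinued".

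The reason given in Section 4.3 for not entering pregnant women is "because the study drugs (Lupron, estrogen, and progesterone) may be associated with birth defects". Section 4.2 separately advises against leuprolide in pregnancy.

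**The concern.** The plan checks for pregnancy on the day of the first Lupron injection but, as far as the text shows, not on the day of the second. That second step is the larger one: a further depot dose and, by inference, the first active hormone capsules. A woman who conceived after Visit 3 and had not recognised it would pass through this step with her last objective test four weeks old. The discontinuation rule can only prevent exposure if the pregnancy is known before dosing. At Visit 6 it is too late to withhold the second injection or the active course.

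The protocol's ground for thinking pregnancy unlikely is also least secure early in this window. Section 1.2 describes an initial stimulation of gonadotropins before suppression, and Section 5.2 expects a stable hypogonadal state only after that flare.

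**Working it through.** The plan states no figure on this point, so the check sets the testing schedule against the dosing schedule.

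**Schedule** (Sections 4.2, 5.2 and 6, Table 1, Appendix C)

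| Visit | Approx. week | Pregnancy test in the text | Drug step |
|---|---|---|---|
| 2 | before treatment | serum hCG | none |
| 3 | 0 | scan-day test | Lupron dose 1, end of visit |
| 4 | between 0 and 4 | none shown | placebo capsules |
| 5 | 4 | none shown | Lupron dose 2; active capsules start (inferred) |
| 6 | 6 | scan-day test | active course ends |

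**Why Visit 5 is taken as the active start.** No table says so by visit number. Section 6 puts dose 2 one month after Visit 3 and lists it at Visit 5. Sections 5.2 and 6 start addback after one month of Lupron alone. Section 6 puts the Visit 6 scan at the end of the two-week addback, and Section 5.7 dispenses capsules in two-week supplies. Table 2 in Section 1.5 ("Table 2. Medication Regimens in previous IND Exempt Protocol and the Proposed Protocol") places dose 2 in the addback column. Together these point to Visit 5.

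**What Table 1 can and cannot show.** Neither copy has a pregnancy-test row, even for the scan-day tests that Section 4.2 requires, so its silence at Visit 5 proves nothing by itself. The finding rests on Section 4.2 tying on-study tests to scan days, and on Visit 5 having no scan.

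**Arithmetic**

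- Gap between tests now, Visit 3 to Visit 6: 6 × 7 = 42 days.
- With a Visit 5 test: 4 × 7 = 28 days, then 2 × 7 = 14 days. The longest gap becomes 28 days.
- Injections with a same-day test: 1 of 2 now (Visit 3), 2 of 2 after the change.
- Tests per woman: 3 (Visits 2, 3, 6) rising to 4. If the Section 4.3 screening test is separate from the Visit 2 serum test, 4 rising to 5.
- Extra tests in total: at most 39 × 1 = 39. If all three withdrawals expected in Section 7.1 occur before Visit 5, 39 − 3 = 36.
- Scheduled exposure from Visit 5 to Visit 6, per woman: one 3.75 mg depot dose, 14 × 4 = 56 mg estradiol and 14 × 400 = 5,600 mg progesterone.
- Planned in-person time at Visit 5 (Table 1): 0.15 h × 60 = 9 minutes at most.

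The documents give neither a pregnancy rate nor a test sensitivity. No number of cases detected or doses averted is therefore calculated.

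**The case against.** **The check may exist where we cannot see it.** Section 5.4 falls within the study-drug chapter, Appendix A is the consent form, Appendix B is a procedures flowchart and Figure 6 is the timeline. None of these can be seen, and any could contain a Visit 5 test. This stands. A reader might infer that the trial does no test at Visit 5; the documents support only that none appears in the visible text.

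**The plan already controls pregnancy.** It has screening and pre-treatment tests, tests on both scan days, required non-hormonal contraception, withdrawal on pregnancy, adverse-event questioning at every contact (Section 8.2) and regular phone and email check-ins (Section 6). A reader might infer that pregnancy is left unmonitored or that the plan contradicts itself. Neither is so: no rule requires a test before every dose. Still, questioning and check-ins can miss an unrecognised pregnancy.

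**The hazard can be overstated.** A reader might cite the statement in Section 1.5 that "several reports suggest an association between intrauterine exposure to female sex hormones and congenital anomalies". That sentence closes a paragraph on combined oral contraceptives, and the same section distinguishes the study hormones from the substituted steroids in many such products. It should not carry the argument. Section 1.2 also notes that "Healthy women undergoing in vitro fertilization (IVF) routinely receive luteal supplementation of 600 mg progesterone daily along with 6 mg oral micronized estradiol", together with GnRH agonists. The daily doses here are two thirds of those (400/600 = 4/6). The case rests instead on the stated exclusion reason in Section 4.3 and the leuprolide advice in Section 4.2.

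**The test has costs and limits.** The team deliberately reduced close contact under COVID-19 (Sections 1.5 and 6), and Visit 5 is otherwise virtual. A self-collected sample saves contact time but is unobserved. The test would miss very recent conceptions and those during addback, and could not undo the first injection. All of this stands and keeps the expected benefit small.

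**Conclusion.** The point holds as a modest safety improvement. On the text we can see, women receive the second Lupron dose about 28 days after their last scheduled pregnancy test, and the next test follows the active course. One added test would give both injections a same-day check and shorten the longest on-treatment gap from about 42 to about 28 days.

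This rests on two things: that the unseen parts hold no such check, and the inference that active capsules start at Visit 5. If that inference failed, the untested second injection would remain. With contraception required and at most 39 women enrolled, few cases can be expected, and no averted harm is claimed. It is not a statistical error, and endpoints and analyses are unaffected.

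**What to change.** In Section 4.2 and its Appendix C copy, require a negative urine pregnancy test before each Lupron injection. Visit 3 is already covered by the scan-day test, so the only new test is at Visit 5, before the injection and before the first active capsules. Keep the Visit 6 test. Add a pregnancy-test row for Visits 2, 3, 5 and 6 to both copies of Table 1. A positive result falls under the existing discontinuation rule, so no new rule is needed. If Section 5.4 or another unseen part already requires the Visit 5 test, the change reduces to stating it in Section 4.2 and Table 1.

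The cost is 36 to 39 urine tests at a visit that is already in person for the injection, plus the wording changes. Testing on the spot may add a few minutes (assumed) to a contact planned at no more than 9. Self-collection before staff arrive avoids most of that, at the price of an unobserved sample.
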